## **Enrollment of Women of Childbearing Potential and Partners**

Although it is highly unlikely that a male or female patient of childbearing potential would be enrolled in this trial, the following criteria must be met for women of childbearing potential and their partners:

- a) Women of childbearing potential must have a negative serum or urine pregnancy test (minimum sensitivity 25 IU/L or equivalent units of HCG) within 24 hours prior to the start of study drug.
- b) Women must not be breastfeeding.
- c) Women of childbearing potential must agree to follow instructions for method(s) of contraception for the duration of treatment with study drug 6 months plus 5 half-lives of study drug (2.5 days) plus 30 days (duration of ovulatory cycle) for a total of 212.5 days post-treatment completion.
- d) Males who are sexually active with women of childbearing potential must agree to follow instructions for method(s) of contraception for the duration of treatment with study drug 6 months plus 5 half-lives of the study drug (2.5 days) plus 90 days (duration of sperm turnover) for a total of 272.5 days post-treatment completion.
- e) Azoospermic males and women of childbearing potential who are continuously not heterosexually active are exempt from contraceptive requirements. However, women of childbearing potential who are continuously not heterosexually active must still undergo pregnancy testing.

Investigators will counsel women of childbearing potential and male subjects who are sexually active with women of childbearing potential on the importance of pregnancy prevention and the implications of an unexpected pregnancy. Investigators will advise women of childbearing potential and male subjects who are sexually active with women of childbearing potential on the use of highly effective methods of contraception. Highly effective methods of contraception have a failure rate of < 1% when used consistently and correctly.

At a minimum, subjects must agree to the use of one method of highly effective contraception as listed below:

- Male condoms with spermicide
- Hormonal methods of contraception including combined oral contraceptive pills, vaginal ring, injectables, implants and hormone-impregnated intrauterine devices (IUDs) by women of childbearing potential subject. Female partners of male subjects participating in the study may use hormone based contraceptives as one of the acceptable methods of contraception since they will not be receiving study drug.
- IUDs

- Tubal ligation
- Vasectomy
- Complete Abstinence\*

\*Complete abstinence is defined as complete avoidance of heterosexual intercourse and is an acceptable form of contraception for all study drugs. Female subjects must continue to have pregnancy tests. Acceptable alternative methods of highly effective contraception must be discussed in the event that the subject chooses to forego complete abstinence

A woman of childbearing potential is defined as any female who has experienced menarche and who has not undergone surgical sterilization (hysterectomy or bilateral oophorectomy) and is not postmenopausal. Menopause is defined as 12 months of amenorrhea in a woman over age 45 years, in the absence of other biological or physiological causes. In addition, females under the age of 55 years must have a serum follicle stimulating hormone, (FSH) level > 40mIU/mL to confirm menopause.

\*Females treated with hormone replacement therapy, (HRT) are likely to have artificially suppressed FSH levels and may require a washout period in order to obtain a physiologic FSH level. The duration of the washout period is a function of the type of HRT used. The duration of the washout period below are suggested guidelines and the investigators should use their judgement in checking serum FSH levels. If the serum FSH level is >40 mIU/ml at any time during the washout period, the woman can be considered postmenopausal:

- 1 week minimum for vaginal hormonal products (rings, creams, gels)
- 4 week minimum for transdermal products
- 8 week minimum for oral products

Other parenteral products may require washout periods as long as 6 months.

### **Screening Procedures**

When a potential study subject is identified, the following screening procedures will be followed:

1. The Principal Investigator or designee at the study site where the potentially eligible patient is receiving care will be contacted by the responsible provider to initiate screening.
2. The Principal Investigator or designee will confirm that patient is > 18 years of age or older, has MM, and is receiving an IMiD (i.e., thalidomide [Thalomid], lenalidomide [Revlimid], and pomalidomide [Pomalyst]).

3. The Principal Investigator or designee will also confirm the absence of all exclusion criteria.
4. The Principal Investigator or designee will provide the potential study subject with the study Informed Consent Form to review, sign, and date. Informed consent must be obtained from a subject with the capacity for medical decision-making and/or the subject's legally authorized representative. The process for obtaining informed consent must be in compliance with the local ethics committee guidelines and policies. Informed consent may be obtained by the Principal Investigator, co-investigators, study coordinators, or an appointed designee. Potential study subjects will not be enrolled if informed consent cannot be obtained. A copy of the signed Informed Consent Form must be provided to the subject or the subject's legally authorized representative. Signed Informed Consent Forms must remain in each subject's study file and must be available for verification at all times.
5. The study coordinator will enter the patient demographic data into the screening portion of the electronic case report form (eCRF).
6. **Subjects who agree to participate in the study and sign the Informed Consent Form will be considered for enrollment in the study and should undergo baseline data acquisition** which includes:
  - a. History and physical examination
  - b. Serum ( $\beta$ -HCG) or urine pregnancy test (u-HCG) for women of child-bearing potential
7. If the potential study subject does not meet all of the inclusion criteria or meets any of the exclusion criteria, the rationale for exclusion from the study will be recorded in the screening section of the electronic case report form (eCRF).

### **Treatment Description**

Patients will begin prophylactic anticoagulation within 3 weeks of passing the screening procedure. Patients with MM receiving IMiDs will be assigned to receive apixaban 2.5 mg orally twice daily for primary prevention of VTE for a duration of 6 months.

If patients come off IMiD therapy during the 6-month study period due to progression of disease or therapy failure, apixaban will be discontinued.

If during the study period the patient requires an invasive procedure or surgery that necessitates the discontinuation of anticoagulation (study drug), apixaban should be held as per the prescribing guidelines (**Appendix**,

[http://packageinserts.bms.com/pi/pi\\_eliquis.pdf](http://packageinserts.bms.com/pi/pi_eliquis.pdf)). If appropriate based on the judgment of the responsible clinician, apixaban should be restarted when safe to do so postoperatively.

## **Safety Outcomes**

### **Primary Safety Outcome**

The primary safety outcome is the 6-month rate of major and clinically relevant non-major bleeding in MM patients receiving IMiDs who are prescribed apixaban 2.5 mg orally twice daily for primary prevention of VTE.

Using the ISTH classification, bleeding is defined as major if it is overt and associated with a decrease in the hemoglobin level of 2 g/dL or more, requires the transfusion of 2 or more units of blood, occurs into a critical site, or contributes to death (12).

Using the ISTH classification, clinically relevant nonmajor bleeding is defined as overt bleeding not meeting the criteria for major bleeding but associated with medical intervention, surgical intervention, or interruption of the study drug.

### **Secondary Safety Outcome**

All-cause mortality at 6 months will be recorded. Cause of death will be classified as related to cancer, myocardial infarction, PE, other cardiovascular or other disease state. Death will be attributed to PE if there is evidence to support an association with PE.

## **Efficacy Outcomes**

### **Primary Efficacy Outcome**

The primary efficacy outcome is the 6-month rate of symptomatic VTE in MM patients receiving IMiDs who are prescribed apixaban 2.5 mg orally twice daily for primary prevention of VTE.

DVT is diagnosed as a noncompressible venous segment or segments on ultrasonography or a filling defect on computed tomographic (CT) venography, magnetic resonance (MR) venography, or contrast venography.

PE is diagnosed on the basis of a mismatched perfusion defects on ventilation perfusion scan, the presence of a pulmonary artery filling defect on contrast-

enhanced chest CT, a finding of intraluminal filling defect on invasive pulmonary angiography, or evidence of PE at autopsy.

## Secondary Efficacy Outcome

MM patients have an increased risk of atherothrombotic events, including myocardial infarction and stroke. The risk of atherothrombotic events is further increased with IMiDs. Accordingly, the 6-month rates of myocardial infarction and stroke will also be calculated.

An acute MI is defined as the presence of at least 2 of the 3 following conditions (13):

- The detection of a rise and/or fall of cardiac biomarkers, with at least one of the values being elevated [preferably cardiac troponin (cTn) with at least one value above the 99th percentile upper reference limit] and with at least one of the following:
  - (1) symptoms of myocardial ischemia;
  - (2) new (or presumably new) significant ST-segment/T-wave changes or left bundle branch block;
  - (3) development of pathological Q waves on ECG;
  - (4) new loss of viable myocardium or regional wall motion abnormality by imaging;
  - (5) identification of intracoronary thrombus by angiography or autopsy

An acute stroke was defined as a new, focal neurologic deficit of sudden onset, lasting at least 24 hours, not due to a readily identifiable nonvascular cause (i.e. brain tumor, trauma), as confirmed by a neurologist (2). All strokes during the study were assessed by imaging or autopsy, and classified as primary hemorrhagic, non-hemorrhagic, infarction with hemorrhagic conversion, or unknown, as defined by the American College of Cardiology.

- **Primary hemorrhagic:** a stroke with documentation on imaging (e.g., CT scan or magnetic resonance imaging) of hemorrhage in the cerebral parenchyma, or subarachnoid hemorrhage. Evidence of hemorrhagic stroke obtained from lumbar puncture, neurosurgery, or autopsy can also confirm the diagnosis.
- **Non-hemorrhagic:** an ischemic focal neurological deficit (and not due to hemorrhage) that appears and is still partially evident at 24 hours.
- **Infarction with hemorrhagic conversion:** no evidence of hemorrhage on an initial scan, but found on a subsequent scan and is clinically relevant to the event, as determined by a neurologist.
- **Unknown type/no imaging performed:** the type of stroke could not be determined by imaging or other means (lumbar puncture, neurosurgery).

## Follow-up

## Follow-Up Evaluation

Routine follow-up visits with study personnel will not be required. Study patients will be encouraged to follow-up with their primary care providers and other appropriate clinicians, including oncologists. Data regarding study outcomes will be abstracted from the Electronic Health Record.

We will assess medication adherence via pill count. Medication adherence will be calculated as the total number of doses taken divided by the total number of doses prescribed ( $(x / 336) \times 100 = \text{medication adherence } [\%]$ ).

Subjects will be given a study diary to fill out at home each day. Subjects will write down the time they take their study drug and any side effects. The study diary will be collected at a regularly scheduled office visit at conclusion of the study period.

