## Subject Retention, Withdrawal, and Termination

Continued participation of study subjects will be encouraged at the time of outpatient evaluation through the 6-month follow-up interval. However, study subjects will be informed that they retain the right to withdraw from the study at any time without compromise to their current or subsequent medical care. Subjects will be terminated from the study if they expire or elect to withdraw.

If study subjects elect to withdraw, they will be asked for permission to do the following:

1. Be contacted by telephone **AND**
2. Have a family member contacted **AND**
3. Have their physicians contacted

Withdrawal criteria will include:

1. Patient requests to withdraw
2. Reasons related to SAE:
  - a. Initiating or continuing study drug places the subject at undue hazard as determined by the Investigator;
  - b. SAE or other safety concern that is related to study drug treatment;
  - c. Major or life-threatening bleeding (as defined in the protocol)
  - d. ALT or AST  $\geq 3$  ULN, if suspected to be due to the study drug
  - e. Calculated CrCL decreased to  $< 30$  mL/min confirmed by repeat testing at least one week later, or need for dialysis
  - f. Subjects in whom multiple myeloma is felt to be refractory to therapy or who have transitioned to a palliative treatment strategy
3. Pregnancy;
4. Patient develops severe hepatic impairment (Child-Pugh class C) during the trial;

5. Death;
6. Lost to follow-up (every attempt will be made by the Investigator not to have subjects “lost to follow-up”);
7. Study terminated by sponsor (termination of all or part of the study by the sponsor, in concert with the study leadership)

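### Adherence is defined as doses taken over doses prescribed but divided by a constant 336 (168 days), which conflicts with the 180-day course implied elsewhere and with directed early stops

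*Combined protocol and SAP*

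**What the plan says.** Follow-Up Evaluation says adherence will be assessed by pill count and that "Medication adherence will be calculated as the total number of doses taken divided by the total number of doses prescribed". The formula beside that sentence divides the doses taken by 336 and multiplies by 100, with no adjustment for any patient. The same section gives each patient a daily diary for dosing times.

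Treatment Description assigns "apixaban 2.5 mg orally twice daily for primary prevention of VTE for a duration of 6 months". It also ends or interrupts dosing for some patients. One rule is that "If patients come off IMiD therapy during the 6-month study period due to progression of disease or therapy failure, apixaban will be discontinued". For invasive procedures that require anticoagulation to be stopped, "apixaban should be held as per the prescribing guidelines". Subject Retention, Withdrawal, and Termination adds further withdrawal criteria, including major bleeding and "Subjects in whom multiple myeloma is felt to be refractory to therapy or who have transitioned to a palliative treatment strategy".

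Enrollment of Women of Childbearing Potential and Partners adds 6 months of treatment, 2.5 days and 30 days "for a total of 212.5 days post-treatment completion" for women. For men it adds 6 months, 2.5 days and 90 days "for a total of 272.5 days post-treatment completion".

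The inclusion criteria require a plan for at least 6 cycles of IMiD therapy. No cycle length is given.

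**The concern.** The words and the formula describe the same quantity only for a patient who was prescribed exactly 168 days of twice-daily dosing. Two problems follow.

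First, 168 days is not the length that the documents' own sums give to 6 months. If the course is longer than 168 days, completers can read above 100% and missed doses can disappear behind an apparently perfect score.

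Second, whichever length was meant, doses stop being prescribed when the protocol takes a patient off drug, yet the denominator stays at 336. Such patients are foreseen: the Statistical Analysis Plan section keeps anyone with at least 2 IMiD cycles in a modified intention-to-treat analysis.

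What is at stake is how the adherence figure is read. The Introduction and Ethical Considerations use weaker adherence to injectable regimens as part of the case for an oral drug, and the study is meant to inform a larger randomized trial. A percentage that mixes directed stops with missed doses serves that purpose badly.

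**Working it through.** **Inputs.** Two doses a day for 6 months (Treatment Description); denominator 336 (Follow-Up Evaluation); totals of 212.5 and 272.5 days with their stated components (section on women of childbearing potential and partners); at least 6 planned IMiD cycles (inclusion criteria).

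**1. What 336 stands for.** 336 / 2 = 168 days, or 24 weeks. It also equals 2 × 28 × 6, so it would fit six 28-day cycles. The 28 days is an assumption, because the documents state no cycle length and do not tie the duration of apixaban to cycles.

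**2. What 6 months is elsewhere.** Women: 212.5 − 2.5 − 30 = 180 days. Men: 272.5 − 2.5 − 90 = 180 days. At two doses a day this is 360 doses. The 180 is back-calculated: the section adds the treatment period into the total and then labels the total as time after treatment. Six calendar months of 181 to 184 days would give 362 to 368 doses. Only 168 days gives 336.

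**3. Effect on completers if the course is 180 days.**
- All doses taken: 360 / 336 = 107.1% (368 / 336 = 109.5% at 184 days).
- True adherence of 90%: 0.90 × 360 = 324; 324 / 336 = 96.4%.
- Displayed 100%: 336 taken of 360, so 360 − 336 = 24 missed doses (12 days) and true adherence of 336 / 360 = 93.3%.

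If the course is 168 days, completers read correctly.

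**4. Effect of a directed stop, every dose taken until then.** On each patient's own prescribed doses the answer is 100% in every row.

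| Last day of dosing | Doses taken | Divided by 336 | Divided by 360 |
|---|---|---|---|
| 30 | 60 | 17.9% | 16.7% |
| 90 | 180 | 53.6% | 50.0% |
| 120 | 240 | 71.4% | 66.7% |

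Replacing one constant with the other therefore does not cure this part.

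**5. Effect of a directed hold.** A 7-day hold is 14 doses: 14 / 336 = 4.2 points, or 14 / 360 = 3.9 points.

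**The case against.** The best defence of 336 is that a 24-week course of six 28-day cycles was intended. That is possible, and if so completers are scored correctly. The three sections would still disagree on the length of treatment, and the early-stop problem would be untouched.

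A second defence is that the prescribed doses mean the course assigned at entry. A planned-course denominator is a recognisable measure of how much of the intended treatment was taken, and it sits naturally beside an intention-to-treat analysis. This partly stands: the document does not say which meaning applies. But a single figure cannot serve as both completion and adherence, and reporting the two separately keeps the useful part of this reading.

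Third, there are safeguards. The diary can show missed doses and may date holds. The case report form asks whether the full 6 months was completed and, if not, why. A low value could therefore be explained patient by patient, although the summary percentage would still be wrong. The documents also do not say how many tablets are dispensed, and readings above 100% need more than 336 doses to be dispensed and taken.

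A reader might infer more than the documents support:
- That patients stopped early would be classed as poorly adherent. No cut-off or label is given; only a lower percentage follows.
- That the cohort average is biased by a known amount. The documents give no expected number or timing of directed stops.
- That the case report form lacks the fields needed. The list of stop reasons appears to be cut off in the text available, so absence cannot be concluded.

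**Conclusion.** The formula is wrong as written, and the point is minor. The mismatch between 336 and 360 is plain arithmetic, subject to the 180 days being derived from the contraception totals and not stated. On a 180-day course, full adherence reads 107% and 100% can reflect 24 missed doses. Under either length, a fully adherent patient directed to stop at day 90 reads 54%. That second part assumes that prescribing ends when the protocol directs the drug to stop.

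It would be a mistake to read this as a threat to the trial's main results. Adherence is not among the safety or efficacy outcomes and is not named in the Statistical Analysis Plan section, so no bleeding or VTE rate changes. Nor do the documents show which treatment length is correct; they show only that the sections disagree.

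**What to change.** 1. Reconcile Follow-Up Evaluation, Treatment Description and the contraception totals on the length of the treatment period in days. Which length applies is for the sponsor to state.
2. Replace 336 with each patient's prescribed doses: 2 × the days from the start date on the case report form to the earliest of the planned end of treatment, a directed stop, or death. Subtract directed holds where the diary or records date them.
3. Report the share of the planned course completed as a separate figure. Patients who stop by choice keep the planned course as denominator, so their stops stay visible: a day-60 stop after perfect dosing reads 120 / 360 = 33%, or 120 / 336 = 36% on a 168-day course.

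The cost is a change of wording and slightly more derivation work, since start and stop dates are already collected. The remaining weakness is that holds without dates stay in the denominator, at about 4 points per 7-day hold. No new data collection is needed.

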## Subject Retention, Withdrawal, and Termination

Continued participation of study subjects will be encouraged at the time of outpatient evaluation through the 6-month follow-up interval. However, study subjects will be informed that they retain the right to withdraw from the study at any time without compromise to their current or subsequent medical care. Subjects will be terminated from the study if they expire or elect to withdraw.

If study subjects elect to withdraw, they will be asked for permission to do the following:

1. Be contacted by telephone **AND**
2. Have a family member contacted **AND**
3. Have their physicians contacted

Withdrawal criteria will include:

1. Patient requests to withdraw
2. Reasons related to SAE:
  - a. Initiating or continuing study drug places the subject at undue hazard as determined by the Investigator;
  - b. SAE or other safety concern that is related to study drug treatment;
  - c. Major or life-threatening bleeding (as defined in the protocol)
  - d. ALT or AST  $\geq 3$  ULN, if suspected to be due to the study drug
  - e. Calculated CrCL decreased to  $< 30$  mL/min confirmed by repeat testing at least one week later, or need for dialysis
  - f. Subjects in whom multiple myeloma is felt to be refractory to therapy or who have transitioned to a palliative treatment strategy
3. Pregnancy;
4. Patient develops severe hepatic impairment (Child-Pugh class C) during the trial;

5. Death;
6. Lost to follow-up (every attempt will be made by the Investigator not to have subjects “lost to follow-up”);
7. Study terminated by sponsor (termination of all or part of the study by the sponsor, in concert with the study leadership)

## **Assessment and Reporting of Adverse Events**

### **Definitions**

#### *Adverse events*

An adverse event (AE) is defined as any new untoward medical occurrence or worsening of a pre existing medical condition in a patient or clinical investigation subject administered an investigational (medicinal) product and that does not necessarily have a causal relationship with this treatment. An AE can therefore be any unfavorable and unintended sign (including an abnormal laboratory finding, for example), symptom, or disease temporally associated with the use of investigational product, whether or not considered related to the investigational product. The causal relationship to study drug is determined by a physician and should be used to assess all AEs.

Adverse events can be spontaneously reported or elicited during open-ended questioning, examination, or evaluation of a subject. (In order to prevent reporting bias, subjects should not be questioned regarding the specific occurrence of one or more adverse events).

All SAEs that occur following the subject’s written consent to participate in the study through 30 days of discontinuation of dosing will be reported to BMS Worldwide Safety.

